NOTE: Participation in this study is limited to pre-approved, credentialed surgeons (see S1011 protocol abstract page on <http://swog.org> for list of pre-approved, credentialed surgeons and Section 12.1 for credentialing process).

** For patients who did not receive neoadjuvant chemotherapy, post operative adjuvant chemotherapy for pT any, N+ or pT3-4, N0 is strongly recommended but not required and will be left up to the treating physician. We strongly encourage patient evaluation for adjuvant chemotherapy in a multidisciplinary session with the treating urologic surgeon and GU medical oncologist coordinating decision making and administration of chemotherapy.

1.0 OBJECTIVES

1.1 Primary Objective

- a. To compare disease-free survival (DFS) in patients undergoing radical cystectomy for muscle-invasive urothelial carcinoma of the bladder (UCB) treated with radical cystectomy and extended pelvic lymph node dissection (PLND) compared to radical cystectomy and standard pelvic lymphadenectomy.

1.2 Secondary Objectives

- a. To compare overall survival (OS) in patients randomized to extended PLND versus those randomized to standard pelvic lymphadenectomy.
- b. To evaluate operative time, whether or not nerve sparing was performed, intra-operative, peri-operative and 90 day morbidity and mortality, length of hospital stay, histology (pure urothelial versus mixed), lymph node counts and lymph node density, adjuvant chemotherapy received, and local and retroperitoneal soft tissue recurrence in patients randomized to extended PLND versus those randomized to standard pelvic lymphadenectomy. Proximal extent of node dissection in those patients randomized to extended PLND will be evaluated as well.

1.3 Translational Medicine Objectives

- a. To bank paraffin embedded blocks or slides of the primary tumor for future translational medicine studies including markers of epithelial and mesenchymal transition and correlate these findings with pathologic T stage and node metastasis as well as DFS and OS.
- b. To determine the prognostic value of several putative markers of the pre-metastatic niche in muscle-invasive bladder cancer, including (1) extent of neutrophil infiltration, (2) phosphorylated signal transducer and activator of transcription 3 (pSTAT3) expression, (3) vascular endothelial growth factor 1 (VEGFR1) expression, and (4) macrophage infiltration.
- c. To evaluate whether the prevalence of the pre-metastatic niche is different amongst patients that received neoadjuvant chemotherapy as compared to those who did not.

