11.4 Analysis of Translational Medicine Endpoints

Aim: To identify the relationship between expression of markers of epithelial mesenchymal transition in the primary bladder tumor with local tumor stage, the burden of lymph node metastases, and the likelihood of disease recurrence among patients undergoing cystectomy for muscle invasive bladder cancer.

Tumor marker expression will be measured as a function of proportion of cells staining and intensity of staining (IHC studies) and/or relative level of mRNA expression (compared to internal controls). Associations between marker expression and nodal status (positive vs negative, low disease burden versus high disease burden), and neoadjuvant chemotherapy will be tested using chi square test. Kaplan Meier estimates of survival and DFS based on marker expression will be performed and corresponding survival and DFS curves will be compared using log rank testing. Cox proportional hazards regression analysis will be performed to estimate hazard ratios for progression free survival. Those analysis will be repeated, stratified by whether patients received

neoadjuvant and adjuvant chemotherapy. Where associations look different by strata, formal tests of interaction will be performed in order to assess markers associated with chemoresistance.

If we assume that 70% of patients will have adequate tissue samples available based on prior SWOG experience with surgical trials, then we will have 396 samples (198 per arm). The following table provides estimate of the minimally detectable hazard ratio for disease-free survival for those with the tissue marker of interest vs. those without. These calculations assume 5 years of accrual, 3 additional years of follow-up, median DFS of 3-year in those with the marker, a two-sided alpha=0.05 and 80% statistical power. Similar survival hazard ratios can be detected with two additional years of follow-up. These calculations also assume there is no interaction between the marker of interest and the randomized treatment assignment (type of lymph node dissection).

	Prevalence of Tissue Marker		
	10%	20%	30%
DFS Hazard Ratio for Those with versus Those without the Marker of Interest	1.82	1.57	1.50

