The 'seed-and-soil' hypothesis was proposed by Paget in 1889, and suggests that the biological characteristics of certain tissues may foster invasion and growth of metastases. (23) Identification of these susceptible areas, termed pre-metastatic niches, has numerous possible clinical applications. For instance, patients with more abundant niches may have increased metastatic potential – niche prevalence could therefore serve as a personalized supplement to current prognostic models. (24)

In bladder cancer, we have generated preliminary data suggesting that the pre-metastatic niche may be marked by neutrophils (i.e., CD15⁺ cells). Specifically, we have assessed benign nodal tissue derived from 20 patients with muscle-invasive bladder cancer. Through an IRB-approved protocol (COH IRB 11210), benign lymph node tissue collected at the time of cystectomy from a cohort of 20 patients was obtained. These patients had (1) a pathologically verified diagnosis of muscle invasive disease prior to cystectomy, (2) pT2a-T4N0 disease determined at the time of cystectomy, (3) no radiographic evidence of metastasis prior to cystectomy, and (4) available paraffin-embedded sections

encompassing both primary tumor and benign lymph nodes. From these patients, 4 μ m sections of benign lymph node tissue were stained with monoclonal antibodies directed at VEGFR1 (ImClone Systems) and CD15 (a human neutrophil marker; Abcam). Stained sections for pSTAT3 (Santa Cruz Biotechnology) were performed, since recent data suggest the potential role of phosphorylated Signal transducer and activator of transcription 3 (pSTAT3) in mediating neutrophil recruitment to pre-metastatic sites. (25) Co-localization of VEGFR1 and CD68⁺ macrophages was observed, and sections were stained with a monoclonal antibody directed at CD68 (Signet). Image Pro Plus software was used to count positive cells and an average count across the 8-100x fields was used for statistical analyses. The median age of this cohort was 70 (range, 40-86), and the cohort included a relatively balanced number of patients with clinical stage 2 and 3 disease (11 patients and 9 patients, respectively). Only 1 patient had received neoadjuvant chemotherapy in this cohort, and 2 patients had received adjuvant treatment (all 3 patients received cisplatin/gemcitabine as their cytotoxic regimen).

[figure not shown]

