Several correlative studies have been built into the original protocol. The statistical considerations for the current study are slightly different, as we plan to incorporate a testing and validation cohort. We expect that 395 patients will have usable lymph node samples as specified in the protocol (assuming that tissue is available for 70% of study participants). The testing cohort will be comprised of the first half of these patients, or approximately 200 patients, and the results from the second 200 patients will be used for validating the results. On a case by case basis, some patients who are found to be ineligible for the clinical trial due to reasons other than pathology may be used for these analyses.

The underlying hypothesis for the correlative studies associated with this aim is that biomarker expression levels (i.e., (CD15, pSTAT3, VEGFR1 and CD68 cell counts in the benign nodal tissue) may predict clinical outcome (i.e., DFS). For each biomarker, recursive partitioning will be used to determine the cutoff value of average cell count that maximally distinguishes DFS within the training cohort. These cutoffs will be examined in the validation cohort.

[Table 1](#) provides an estimate of the minimally detectable hazard ratio for DFS for those with an elevated biomarker expression level (i.e., high CD15

	Prevalence of "High" Biomarker Expression Level				
	10%	20%	30%	40%	50%
DFS HR	2.40	1.93	1.80	1.74	1.73

Table 1. Minimally detectable hazard ratio (HR) for DFS for those with "high" biomarker expression versus those with "low" biomarker expression. Assuming 80% statistical power, 2-sided alpha of 0.05, and 200 patients in the training set (same power for the 200 patients in the validation set).

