expression) relative those with a low biomarker expression level. These effect sizes apply equally to the training and validation subsets since the sample size will be the same for both. The designation of "high" and "low" biomarker expression levels will be based on the cutoffs designated in the training cohort. These calculations assume 5 years of accrual, 3 additional years of follow-up, median 3-year DFS of 50% in those with "high" biomarker expression, a two-sided alpha of 0.05, and 80% statistical power. These calculations further assume that there is no interaction between the marker of interest and the randomized treatment assignment (type of lymph node dissection). Because all currently enrolling patients are being offered participation in the banking of their lymph node tissue, there will be no loss of sample size for this recently activated trial.

In some cases, there may be a combination of biomarkers that have a multiplicative effect on the risk of relapse. Classification and regression trees to assess the potential multiplicative effect amongst markers and form prognostic groups based on these algorithms will be explored. Prognostic models using traditional clinical factors such as clinical stage,

pathologic stage, age, receipt of neoadjuvant chemotherapy and performance status to predict disease-free survival will be developed in the training set and the area under the curve (AUC) will be calculated in the validation set. (43) Then, the model that also incorporates markers of the pre-metastatic niche (identified in the training set) will also be added to the model and the AUC will again be estimated. A comparison of the traditional AUC to the niche AUC will be made to evaluate whether these biomarker expression factors contribute to the DFS prognosis in this patient population.

Bibliography for 18.2

- 1 Fidler, I.J., Critical factors in the biology of human cancer metastasis: twenty-eighth G.H.A. Clowes memorial award lecture. *Cancer Res* 50(19):6130-8, 1990.)

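### Appendix 18.2b chooses and checks each niche-marker cutoff on DFS with neoadjuvant-treated and untreated patients pooled; if marker and chemotherapy are associated, a real marker can be masked and false validation of a cutoff can rise

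*Combined protocol and SAP*

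**What the plan says.** Section 1.3 sets two niche objectives. Objective b concerns the prognostic value of four markers (neutrophil infiltration, pSTAT3, VEGFR1, macrophage infiltration). Objective c is "To evaluate whether the prevalence of the pre-metastatic niche is different amongst patients that received neoadjuvant chemotherapy as compared to those who did not".

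The statistical plan in Appendix 18.2b divides the usable patients by order of entry: "The testing cohort will be comprised of the first half of these patients, or approximately 200 patients", with the second 200 for validation. For each marker, "recursive partitioning will be used to determine the cutoff value of average cell count that maximally distinguishes DFS within the training cohort". Of validation it says only "These cutoffs will be examined in the validation cohort". Neither step mentions chemotherapy.

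Chemotherapy enters later in the same appendix. A clinical model using stage, age, "receipt of neoadjuvant chemotherapy and performance status to predict disease-free survival" is built in the training set. The niche markers identified in training are then added, and the two AUCs are compared.

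Section 6.0 makes neoadjuvant chemotherapy a randomization stratum. Section 11.4 tests associations of marker expression with nodal status "and neoadjuvant chemotherapy will be tested using chi square test". It also repeats the survival analyses stratified by chemotherapy and plans interaction tests where strata look different. All of this stands under an aim about EMT markers in the primary tumor.

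**The concern.** A factor associated with both a marker and DFS confounds the unadjusted marker–DFS relation. The plan asks whether the first link exists (1.3c) and acts as if the second does, by stratifying randomization on chemotherapy and using it as a DFS predictor. A cutoff search that looks only for the largest DFS separation would then respond to the mixture of marker and chemotherapy. The validation half has the same mixture, so repeating the pooled comparison there does not remove the distortion.

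The error can go either way. Suppose high counts mean worse DFS and are commoner in treated patients, and treated patients do better. The two effects then offset each other, and a true niche marker may be dropped. With other sign combinations, a marker with no effect of its own can pass the cutoff check. The pilot data cannot settle the matter: "Only 1 patient had received neoadjuvant chemotherapy in this cohort", out of 20.

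**Working it through.** **The plan's own table.** Appendix 18.2b gives detectable HRs of 2.40, 1.93, 1.80, 1.74 and 1.73 at marker prevalences of 10–50%: "Assuming 80% statistical power, 2-sided alpha of 0.05, and 200 patients in the training set". It assumes median DFS of 3 years in the high group, 5 years of accrual and 3 of follow-up. With exponential DFS, the event probability is 1 − (e^(−3λ) − e^(−8λ))/(5λ). At 30% prevalence and HR 1.80:
- high group: λ = ln 2/3 = 0.231, probability 0.70, 60 × 0.70 = 42.2 events;
- low group: λ = 0.128, probability 0.50, 140 × 0.50 = 69.7 events;
- z = ln 1.80/√(1/42.2 + 1/69.7) = 3.01, and power = Φ(3.01 − 1.96) = 85%.

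This Wald form needs HRs of only 2.25, 1.85, 1.72, 1.67 and 1.67 for 80% power. At 85% it matches the table to within 0.01. That label is a separate matter. What counts here is that the table makes no allowance for chemotherapy.

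**First-order size of masking.** At a fixed cutoff, the bias in the log HR is about [P(chemo | high) − P(chemo | low)] × ln(HR of chemotherapy). Take 50% treated, the working split in 11.4 (35% + 15%). Assumed inputs are niche-high shares by treatment and a chemotherapy HR of 0.7 or 0.5. Start from the table's HR of 1.74, with its 80% taken at face value (z = 2.80, ln 1.74 = 0.554).
- Mild: high in 50% of treated and 35% of untreated patients, HR 0.7. Difference 0.588 − 0.435 = 0.153; bias 0.153 × (−0.357) = −0.055; apparent HR e^0.499 = 1.65; power Φ(2.80 × 0.499/0.554 − 1.96) = 71%.
- Strong: 60% and 30%, HR 0.5. Difference 0.667 − 0.364 = 0.303; bias 0.303 × (−0.693) = −0.210; apparent HR 1.41; power 41%.

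**Simulating the search and the check.**
- From the documents: 200 + 200 patients, 5 + 3 years, 50% treated, and 55% 3-year DFS (the no-marker figure in 11.4), used here for untreated marker-low patients.
- Assumed: normally distributed marker, raised by the stated shift in treated patients; the chemotherapy HR; for a real marker, hazard × 1.8 above 0.5 SD.
- Cutoff: the largest log-rank statistic over 33 points between the 10th and 90th percentiles.
- Validated: z > 1.96 in the same direction in the second half, so nominally 2.5% for a null marker.
- 2,000 runs per row, standard error at most √(0.25/2000) = 1.1 points.

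| Shift (SD) | Chemo HR | Real marker: pooled / stratified | Null marker: pooled / stratified |
|---|---|---|---|
| 0 | 0.7 | 76% / 76% | 4% / 3% |
| 0 | 0.5 | 67% / 71% | 2% / 2% |
| 0.5 | 0.7 | 66% / 76% | 4% / 3% |
| 0.5 | 0.5 | 42% / 71% | 8% / 3% |
| 1 | 0.7 | 55% / 74% | 6% / 2% |
| 1 | 0.5 | 20% / 68% | 19% / 3% |

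With a chemotherapy HR of 2.0, false validation when pooled is 9% at 0.5 SD and 27% at 1 SD.

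Repeat simulations of the real marker at chemotherapy HR 0.7, under similar settings, gave 63–64% against 75% at 0.5 SD, and 45–51% against 66–69% at 1 SD. A run using a two-sided 5% criterion and 60% 3-year DFS gave 5.9% false validation in its mildest case (0.5 SD, HR 0.7) and 20% in its strongest (1 SD, HR 0.5). The stratified figure there was 5–6% throughout, so the mildest case shows no detectable excess.

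**Where the loss arises.** With a 1 SD shift and true HR 1.8 (1,000 runs per scenario), a pooled cutoff with a pooled test validates 51% (chemotherapy HR 0.7) or 18% (HR 0.5). A pooled cutoff with a stratified test gives 66% or 47%. Stratifying both gives 69% or 62%. At HR 0.7 most of the loss comes from the test. At HR 0.5 the badly placed cutoff costs a further 62 − 47 = 15 points that later adjustment does not recover.

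**The case against.** The strongest reply is that the plan does not stop at the cutoff check. Its stated evaluation of added prognostic value is the AUC comparison, and the base model there contains neoadjuvant chemotherapy, stage, age and performance status. A marker that only tracks chemotherapy should add little. This stands, and it blunts the false-positive half: a reader might infer that the plan would report a chemotherapy proxy as an independent niche marker, and the documents do not support that. The safeguard is indirect, however. No test or decision rule is given for the AUC difference, only markers identified in training enter, and the cutoff is already fixed.

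Second, Section 11.4 plans a chemotherapy-stratified repeat and interaction tests. It does, but under the EMT aim. Appendix 18.2b calls its own statistical considerations slightly different and does not carry those analyses over.

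Third, prognostic value need not be adjusted value. That is fair in general. Here, though, the appendix presents the niche as a possible supplement to existing prognostic models, and it lists chemotherapy among the known factors.

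A reader might also infer that an unadjusted comparison for 1.3c is confounded by stage or fitness. That does not hold. The objective asks descriptively whether prevalence differs between the two groups, an unadjusted comparison answers it, and the documents do not attribute any difference to chemotherapy.

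Finally, every size above rests on assumed associations, and the larger ones need a full-SD shift together with a halved or doubled hazard. This also stands.

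**Conclusion.** The point holds in limited form. As written, each cutoff is derived and checked with treated and untreated patients pooled, although the plan asks whether the niche differs by chemotherapy and treats chemotherapy as related to DFS.

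Masking is the less protected risk. With true HR 1.8, chemotherapy HR 0.7 and a shift of 0.5 to 1 SD, validation is about 45–66% pooled and 66–76% stratified; at chemotherapy HR 0.5 the pooled rate is about 18–42%. False validation of a cutoff runs from no detectable excess to 19–20% at 1 SD with HR 0.5, and 27% with HR 2.0. Those rates describe the cutoff check alone, not the later AUC comparison.

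All of this is conditional on a marker–chemotherapy association whose existence, direction and size the documents do not give. The niche study is exploratory, uses optional specimens and awaits funding. The primary DFS comparison is not affected.

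**What to change.** In Appendix 18.2b:
- Choose each cutoff with a splitting statistic stratified by receipt of neoadjuvant chemotherapy, for example a stratified log-rank.
- Test it in the validation half with the same stratification, and report the chemotherapy-adjusted HR as the result for 1.3b.
- State that the chemotherapy-stratified repeat and interaction tests of Section 11.4 also apply to the niche markers.
- Name the analysis for 1.3c. An unadjusted comparison is enough; an adjusted regression is needed only if a difference is to be attributed to chemotherapy.

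Stratifying is not the same as analysing each chemotherapy group separately. With about 100 patients per group, the detectable HR at 30% prevalence would be 2.2–2.3, so the stratified test on all 200 should be the main result.

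The cost is a few sentences and a few lines of code. Neoadjuvant chemotherapy is already recorded for randomization. With no marker–chemotherapy association, the simulations show no loss from stratifying (76% against 76% at chemotherapy HR 0.7; 71% stratified against 67% pooled at 0.5).

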2.0 BACKGROUND

Despite the fact that pelvic lymphadenectomy is performed at the time of radical cystectomy for urothelial carcinoma of the bladder (UCB), there are no data from randomized clinical trials, which define an association between the extent of the lymphadenectomy and disease progression or survival. There is considerable debate regarding the degree of improvement in outcome gained with a more extensive lymphadenectomy for patients undergoing cystectomy for bladder cancer. This is exemplified by the large degree of variability in the extent of dissection and number of nodes removed by urologists. The extent of nodal dissection promoted by many academic centers involves an extended dissection with the upper limit designated by the aortic bifurcation or the inferior mesenteric artery (IMA). (1,2,3,4,5) The average number of lymph nodes removed at these centers is 20-30 lymph nodes. In fact, it has been proposed that a minimum number of lymph nodes (~25) be utilized for quality assurance purposes for patients undergoing this operation. (6) However, in a large multi-institutional trial evaluating the role of neoadjuvant chemotherapy, 9% of patients at major academic centers had no lymph node dissection and 37% underwent a limited dissection (obturator nodes only). (7) Moreover, population-based data from the SEER program cancer registry demonstrates a pervasive lack of enthusiasm for an extended

lymph node dissection with 40% of patients having no lymph nodes recovered during cystectomy. (8) As more attention has been applied to this important quality measure in recent years there has been a modest increase in the number of nodes removed and a decrease in the percent of patients with no node dissection at all. (9)

Data from several retrospective series and one prospective non-randomized cohort suggest that patients undergoing an extended pelvic lymphadenectomy may derive a survival benefit compared to those undergoing a limited pelvic node dissection. (10) However, conclusions drawn from these studies are subject to significant biases inherent in observational studies of surgical procedures. In addition, there is no prospective data regarding the morbidity as a result of the extent of the nodal dissection. We acknowledge that there is a potential for an increase in post-operative morbidity associated with an extended node dissection (possibly related to increased operative time and/or blood loss) that could outweigh any derived benefit. This provides further support for the importance of studying this dilemma in a randomized controlled trial (RCT). In addition, the importance of a RCT to address the extent of nodal dissection in bladder cancer is reflected in the experience of our surgical colleagues in gastric and pancreas cancer.

Gastrectomy with an extended regional (D2) lymphadenectomy is the standard treatment for curable gastric cancer in Asia. However, because of a 10-30% rate of para-aortic node involvement, additional para-aortic nodal dissection (PAND) has been performed in Japan since the 1980s for patients with advanced stage disease. A landmark RCT asked the question of whether the addition of PAND to the D2 lymphadenectomy improved survival for patients with stage T2-4 tumors. (11) The overall incidence of surgery-related complications was 20.9% in the D2 lymphadenectomy group and 28.1% in the group assigned to D2 lymphadenectomy plus PAND ($p = 0.07$). The authors observed no significant differences in recurrence-free or overall survival rates between the two groups. (12)

Similarly, extended lymph node dissections for pancreatic head cancer have been conducted since the 1980s. Several retrospective trials demonstrated improved survival rates for patients undergoing extended nodal dissection. A RCT to assess the difference between a standard and extended nodal dissection was initiated but closed after an interim analysis revealed a poorer survival and increased morbidity in the extended nodal dissection group. (13)

An extended node dissection in patients undergoing cystectomy for bladder cancer may offer a survival benefit compared to a standard node dissection via more complete tumor eradication, improved staging and thus identifying patients who may benefit from adjuvant chemotherapy, or other theoretical mechanisms. In order to optimize the benefits of an extended node dissection through improved nodal staging, all patients with node metastasis will be strongly advised to receive peri-operative chemotherapy which is currently considered a standard of care in locally advanced urothelial bladder cancer. In addition and in accordance with standard of care, chemotherapy will be strongly recommended for patients found to have advanced pathologic stage (pT3-T4) at cystectomy. Failure to include this stipulation in the trial design could result in biased administration of adjuvant chemotherapy, influenced by which arm the patient was randomized to, and lead to non-informative results.

A poll of centers of excellence suggest that a 10-12% improvement in 3-year DFS (65-67%) for patients in extended lymphadenectomy would be meaningful and establish extended node dissection as the standard of care in this patient population

Since the introduction of MVAC chemotherapy in the 1980s, little progress has been made in improving survival for patients with advanced bladder cancer. Despite a significant improvement in overall survival with administration of peri-operative chemotherapy, the mortality rate for patients undergoing radical cystectomy for UCB approaches 50%. A properly performed lymph node dissection may provide a significant improvement in survival for these patients. Currently the boundaries of a pelvic node dissection for patients undergoing radical cystectomy for UCB are not clear and the urologic community has failed to define a standard template. The literature is replete with various proposed definitions. Defining, a standard nodal dissection for this disease is

critical because the extent of lymph node dissections are increasingly being compromised due to the increasing performance demands placed on the surgeon and the widespread utilization of robotic laparoscopy for this operation. Performing an extended lymph node dissection takes additional time, especially with a robotic laparoscopic approach. Retrospective data and expert opinion are a poor substitute for level I evidence as demonstrated by the findings of RCTs of extended versus standard LND in other solid organ malignancies.

Early reports of radical cystectomy for UCB stressed the high rate of local recurrence that was related, in part, to limited or no dissection of the regional lymph nodes. A greater understanding of the pathways by which UCB progressed, locally and regionally, suggested that a more radical resection might have therapeutic benefit. (14) Jewett hypothesized that 25% to 30% of recurrences in pelvic lymph nodes were due to inadequate lymphadenectomy. In patients undergoing radical cystectomy for UCB the involvement of regional lymph nodes varies from 14% to 40%, thus it is important to define the extent of lymphadenectomy. (15,16,17) Published outcomes following attempts at controlling the regional lymphatics for bladder cancer date back to 1932 when the routine inclusion of a pelvic lymph node dissection at the time of radical cystectomy was initiated. (18)

Controversy regarding the role of lymphadenectomy and the extent of the dissection necessary to obtain maximal tumor control has persisted to the present. Some surgeons recommend that the proximal limit of resection be the level of the bifurcation of the common iliac vessels, since patients with nodal disease superior to this point are thought to be incurable by radical cystectomy. (19) In contrast, others advocate an extended lymph node dissection beyond this point, citing non-randomized data as supportive of a more extensive dissection for improved staging and therapeutic efficacy. (20,21,22)

Several institutional studies have reported improved outcome in patients undergoing an extended lymph node dissection, as defined by the number of lymph nodes identified pathologically. In a study of 447 patients Leissner et al. found a 20% improvement in overall 5- year survival (85% of patients, with organ-confined UCB and greater than or equal to 16 lymph nodes resected survived 5 years compared to 65% of patients with less than or equal to 15 lymph nodes resected). Control of local disease also was superior in patients having a more extensive, compared to a limited nodal resection (17% recurrence compared to 27% recurrence). (23)

At Memorial Sloan-Kettering Cancer Center (MSKCC) the recent experience with radical cystectomy was reviewed to determine the relationship between the extent of lymphadenectomy and staging, disease control and prognosis. (24,25,26) A total of 322 patients with UCB treated by radical cystectomy were reviewed; 258 patients demonstrated no evidence of node involvement while 64 patients had regionally involved lymph nodes. Overall 5-year survival was improved in patients with a greater number of lymph nodes examined regardless of the status of the nodes. For the node-negative group 5-year survivals of 80%, 60%, and 20% were observed for patients with greater than 8, 4 to 7, and 0 to 3 nodes respectively examined following radical cystectomy. For patients with positive node disease, a 50% versus a 20% 5-year survival was seen if greater than versus less than 11 nodes were examined. [name] and colleagues evaluated over 1,000 consecutive patients from 11 different surgeons with different extents of dissection. They observed that the probability of survival continued to rise with increasing numbers of lymph nodes removed up to a threshold of 23 nodes. (27)

Poulsen et al. reported their group's experience with 194 patients treated by either limited or extended lymph node dissection at the time of radical cystectomy. (28) These investigators found a significantly greater number of nodes were removed with the extended dissection (mean 25, range 9 to 67) compared to the limited dissection (mean 14, range 5 to 30). The extended dissection identified a larger percentage of patients with nodal metastases (improved staging). For patients where the primary UCB was confined to the bladder wall, positive nodes were identified in patients having the extended (12.5%) compared to the limited (8.9%) resection. The potential contribution of the extended, compared to limited, dissection to improved cancer control was suggested by a recurrence-free survival at 5 years for the subgroups with tumors confined to the bladder wall (tumor stage pT2b or less) (85% versus 64%, $p < 0.02$) and without evidence of

lymph node metastasis (stage pT3a or less, pN0) (90 % versus 71%, $p < 0.02$). Similarly, local recurrence rates (2% versus 7%) and distant metastatic risk (10% versus 21%) was improved in patients undergoing an extended dissection compared to a limited dissection. These data were corroborated in a recent update of this series which highlighted the fact that one-third of patients had nodal metastasis proximal to the anatomical limits of a node dissection limited to the true pelvis only. (29) In summary these data provide compelling evidence that an extended node dissection may provide a survival benefit for patients undergoing radical cystectomy for UCB. Nevertheless, the inherent aforementioned biases and lack of a control arm limits the conclusions drawn from these studies.

A review of the contemporary cystectomy literature which includes a mix of standard and extended node dissection suggests that a reasonable estimate of disease-free and overall survival associated with standard node dissection for patients with muscle invasive bladder cancer ($\geq T2$) is 55% at 3 years and 55% at 5 years (Table 1 and 2) respectively.

Table 1. Percentage 5 year disease-free survival (DFS) by pathologic stage after radical cystectomy with and without pelvic lymph node metastasis: selected series reporting DFS (2000-2009)

Selected Series	PTS	No. of										N neg	N pos	All pts
		$\leq P1$	P2a	P2	P2b	P3a	P3	P3b	P4a,b					
[name], et al (2001)	300	Not reported												
Stein, et al (2001)	1054	80-88		81		68		47	44	78	35	68		
Madersbacher, et al (2003)	507	76		74			52		36	---	33	62		
Hautmann, et al (2006)	788	90		72			43		28	75	21	66		
Shariat, et al (2006)	888	81		72			44		28	80	35	58		
Ghoneim, et al (2008)	2720	82	75		53		40		29	62	27	56		
Manoharan, et al (2009)	432	81		70			44		16	72	29	64		
Volkmer, et al (2009)	1270	Not reported												62

Table 2. Percentage 5 year overall survival (OS) by pathologic stage after radical cystectomy with and without pelvic lymph node metastasis: selected series reporting OS (2000-2009)

Selected Series	PTS	No. of										N neg	N pos	All pts
		$\leq P1$	P2a	P2	P2b	P3a	P3	P3b	P4a,b					
[name], et al (2001)	300	64	63	59	58	23	26	28	27					45
Stein, et al (2001)	1054	74		72		58		38	33	69	31	66		
Madersbacher, et al (2003)	507	63		63		NS			32	---	26	59		
Hautmann, et al (2006)	788	Not reported												58
Shariat, et al (2006)	888	Not reported												
Ghoneim, et al (2008)	2720	Not reported												
Manoharan, et al (2009)	432	79		60			43		17	69	22	59		

Accrual capability: The Study Chairs have consulted extensively with the major centers of excellence with respect to the overall management of bladder cancer and specifically radical cystectomy as well as surgeons experienced with extended pelvic and iliac lymphadenectomy. Prior to protocol development, the Study Chairs conducted a survey in order to understand practice patterns and willingness and ability to randomize. Commitments were obtained from each of the centers and surgeons surveyed to randomize eligible patients (see [table below](#)). The Study Chairs polled 15 urologists practicing at 7 high-volume centers regarding their interest in participation in this trial. Each center agreed to participate in the study and reported that their anticipated yearly enrollment in this trial would be up to 340-370 patients annually.

Site	Surgeons	# patients potentially eligible/year
Baylor College of Medicine	[name], [name]	40
MD Anderson Cancer Center	[name], [name], [name]	80
Memorial Sloan-Kettering Cancer Center	[name], [name]	50
Oregon Health and Science University	[name]	20-30
University of Southern California	[name], [name]	50-70
University of Texas Southwestern	[name], [name], [name]	50
Washington University School of Medicine	[name], [name]	50
Total	15 surgeons	340-370 year

The size of the eligible population is estimated as 340-370 annually from these centers alone before expanding the trial to additional sites. We anticipate a high acceptance to the trial by patients based on experience with similar trial designs in gastric and esophageal cancers. These are data provided by the surgeons at these sites and represent a high-side estimate of annual accrual. There is an obvious large pool of patients for accrual and commitments from each of these centers to accrue. In order to achieve an accrual rate of 13 patients/month when each of these sites has IRB approval we would require approximately one half of the estimated accrual capability from these sites only. Since this survey, we have obtained commitments from BC Cancer Agency ([name]), Cleveland Clinic ([name]), Rochester ([name]), and University of Texas Health Science Center San Antonio ([name] and [name]). These are high volume SWOG sites. ALLIANCE formally reviewed and unanimously approved the trial. This will facilitate participation from MSKCC and adds vanguard sites at University of Chicago ([name] and [name]), Ohio State ([name]), and UCSF ([name]). ECOG-ACRIN has also agreed to participate and sites expressing interest include Vanderbilt ([name], [name], [name]) and UT Southwestern. If we achieve the accrual required to meet the vanguard feasibility portion of the trial, then the trial would be expanded to other interested centers in SWOG, ALLIANCE and ECOG-ACRIN that meet the credentialing requirements.

Inclusion of Women and Minorities:

This study was designed to include women and minorities, but was not designed to measure differences of intervention effects. The anticipated accrual in the ethnicity/race and sex categories is shown in the table below. Both men and women of all races and ethnic groups are eligible for this study.

Ethnic Category	Females	Males	Total
Hispanic or Latino	10	43	53
Not Hispanic or Latino	116	451	567
Total Ethnic	126	494	620
Racial Category			

Ethnic Category	Females	Males	Total
American Indian or Alaskan Native	0	2	2
Asian	2	9	11
Black or African American	14	36	50
Native Hawaiian or other Pacific Islander	0	0	0
White	110	447	557
Racial Category: Total of all Subjects	126	494	620

